5.2.4 Intraoperative Review

The operating surgeon will conduct breast cancer surgery as usual without using a device to visualize LS301 fluorescence. To prevent bias in data acquisition, a non-operating member of the study team will wear the CVG before the start of surgery to examine the breast tissue and axillary LNs non-invasively and at the completion of the surgery to examine the excised tissue, SLNs and surgical cavity. Findings with the study will be recorded but will not change the standard of care. The operating surgeon will remain blinded to the fluorescence images throughout the operation. The examining surgical team member will wear the CVG and image all six anatomical aspects (superior, inferior, anterior, posterior, medial and lateral) of the surgical specimen as well as the surgical cavity for LS301 fluorescence. The SPY system will be used for confirmatory fluorescence imaging and compared with CVG detection of LS301 fluorescence, during phase 2 of the study.

Detection of LS301 fluorescence at the cut edge of the excised specimen will determine margin positivity and presence of fluorescence in the SLNs indicate presence of metastatic cancer cells. Given that CVG can detect LS301 fluorescence in tumors several millimeters deep, investigators will use pathology data to initially train the system by correlating fluorescence intensity to background ratio with pathologist's margin assessment. The information will then be used in phase 2 to predict margin positivity in the OR. The detection of fluorescence on excised tissue without correlative fluorescence in the tumor cavity after lumpectomy will predict

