If this simple approach fails to accurately identify positive or clean margins, we will use a dual wavelength excitation for the depth-profiling of fluorescence emission. It is well known that light travels through tissue differently across wavelengths due to wavelength-dependent optical properties. When a fluorophore is excited using two wavelengths, the intensity falloff with depth of each wavelength will be related to the depth of the fluorophore. Because both wavelengths are exciting the same fluorophore concentration, the ratio of the fluorescence generated yields the depth of the fluorophore irrespective of concentration accumulated in the tumor tissue. The depth of fluorescence in the resected sample will be estimated using two spectrally separated NIR wavelengths to excite LS301 fluorescence. The ratio of the emitted intensities imaged for both excitation wavelengths will be closer to one when the tumor tissue is at the cut surface. At higher depths the ratio will deviate away from 1 as the shorter wavelength excitation is attenuated more than longer excitation. A depth map of tissue fluorescence will be created and compared to histopathology for determining the accuracy of predicting positive or clear margin status and SLN metastatic status. The dual-wavelength method will initially be implemented as a standalone portable closed box configuration which will then be miniaturized and implemented in the CVG.

The surgically removed tumor mass and SLNs will be pathologically examined under standard protocols. At least 4 specimens from the excised tissue of a patient, two suspected tumor and two suspected healthy tissue per patient will be analyzed.

The tumor specimens generated after breadloafing by the surgical pathologist will be individually imaged using the CVG and the dual-wavelength closed box imaging system before fixation and paraffin embedding to record the fluorescence intensity localization and depth profiles. Pathologist will provide tissue samples that will be sectioned and mounted on slides. The sectioned tissue slides will be imaged for LS301 fluorescence using high-resolution confocal microscopes. These will be compared to standard Hematoxylin & Eosin staining of tumor tissue to verify

LS301 specificity for cancer cells. Additional immunohistochemistry will be performed on these tissue sections to verify or identify LS301-associated biomarkers.

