5.6.2 Determination of LS301-Associated Biomarkers in Breast Cancer Tissue

After surgical removal of the cancer, the second (non-operating) surgeon will examine the tissue with the goggles and an additional ink will be used to identify any LS301 fluorescence in the surgical margin. This surgeon will then use the goggles to procure cores from the inked and sectioned specimens in surgical pathology. These cores will then be frozen and delivered to the biospecimen core for accessioning, processing, and storage. The specimens will then be analyzed to identify LS301-associated biomarkers.

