8.0 STATISTICAL CONSIDERATIONS

8.1 Study Design

A rolling six design which is intended for relatively safe trials and shortening the study duration is proposed for the phase 1 portion ⁷⁴. In the rolling six design, three to six patients can be enrolled to a dose each time. The dose de-escalation occurs when two or more DLT occur at a dose level while dose escalation occurs when 3/3, 4/4, 5/5, 5/6 or 6/6 patients are evaluated without DLT ⁷⁵. Three dose levels will be tested in the phase 1 study, 0.05, 0.075 and 0.10 mg/kg. LS301 will be administered intravenously at a starting dose of 0.05 mg/kg to a cohort of six patients and escalate/de-escalate following the decision rule of the rolling six design. Once six patients have been included at the current dose level, inclusions are suspended until at least five of the six patients have completed the procedure without DLT observed in the evaluation period. MTD is hit where two or more patients out of six at a dose level experience DLT. We do not expect any serious adverse events related to LS301 at the initial Dose Level 1. Once the MTD is determined, an expansion cohort with 9 patients will be tested at the MTD and an optimal imaging dose will be recommended for the subsequent phase 2 trial.

At the completion of the expansion cohort, a single arm phase 2 trial will be performed at the optimal imaging dose. A breast surgeon will perform breast conserving surgery per standard of care. At the completion of the surgery, a second investigator (to reduce bias in data collection) will wear the cancer vision goggle (CVG) to visualize the excised tissue to determine if there are any positive margins based on the presence of LS301 fluorescence. If any positive margins are observed, the subject will be considered to have a positive margin; otherwise, the margin is considered negative. The excised tissue will later be examined by a breast cancer pathologist. Standard pathologic techniques will be used to determine if there are positive margins. Particular attention will be paid to the sites marked following CVG assessment to confirm whether the margin is positive or negative at any of these sites, or positive at other locations not identified by CVG. No interventions will be allowed based on the CVG results.

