8.2.2 Endpoint for Prediction of Positive Margin and Positive SLN Analysis

The primary objective is to assess margin status called by LS301 and CVG in comparison to the gold standard histopathological results. The histopathological results of margin positivity has the following possible results: margin negative, margin positive at LS301 and CVG identified locations, margin positive at LS301 and CVG unidentified locations. Using LS301 and CVG, the exercised tissue will be considered to be margin positive and have ink marked at the identified locations if any positive margins are observed; otherwise, the margin is considered negative. Diagnostic test characteristics (sensitivity and specificity) of LS301 and CVG for margin positivity by histology will be established and margin positivity rate, defined as the proportion of tumors with histopathologically confirmed positive margins but missed by CVG, will be estimated. The secondary endpoint of the phase 2 trial is toxicity.

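### Pathology is steered to the sites that CVG has inked, so the phase 2 reference standard depends on the test under study and sensitivity, specificity and PPV are biased upward

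*Combined protocol and SAP*

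**What the plan says.** Section 8.1 sets the reference standard in two steps. First: "Standard pathologic techniques will be used to determine if there are positive margins". Then: "Particular attention will be paid to the sites marked following CVG assessment to confirm whether the margin is positive or negative" at any of those sites, "or positive at other locations not identified by CVG". Section 5.2.4 likewise says: "The surgically removed tumor mass and SLNs will be pathologically examined under standard protocols".

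The CVG call reaches pathology on the specimen itself. Under section 8.2.2 a CVG-positive specimen will "have ink marked at the identified locations if any positive margins are observed", and section 5.6.2 says "an additional ink will be used to identify any LS301 fluorescence in the surgical margin".

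Masking is stated for one person. Section 5.2.4: "The operating surgeon will remain blinded to the fluorescence images throughout the operation". The CVG reader is a separate investigator, which section 8.1 explains as a guard against bias. No section masks the pathologist, fixes the number of sections per specimen face, or requires marked and unmarked margin to be worked up alike.

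Section 8.3.2 treats histopathology as the gold standard and defines sensitivity as n22/(n13+n22), specificity as n11/(n11+n21), PPV as n22/(n21+n22), NPV as n11/(n11+n13), and the margin positivity rate as n13 over all tumours.

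**The concern.** A diagnostic accuracy estimate needs a reference standard whose chance of finding disease does not depend on the index test result. Here a CVG-positive site carries ink and gets particular attention, while a CVG-negative specimen carries no CVG ink and gets the standard examination. If closer attention finds any small focus that the standard examination would have missed, it finds it only where CVG was positive. The find then counts as a CVG success.

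Margin prediction is part of the phase 2 primary objective (sections 2.1 and 8.2.2), and section 8.4 expects only 14 positive margins among 88 patients. With so few positives, one or two reclassified tumours can change the conclusion on sensitivity. No later analysis can remove the bias, because the plan does not record what the standard examination alone would have found at the marked sites.

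**Working it through.** **Inputs.** From section 8.4: N = 88, 14 expected positive margins (so 74 negative), sensitivity 0.70 against 0.95, one-sided exact binomial test at 0.05, and a 15.5% margin positivity rate. The estimators are from section 8.3.2. The detection rates are assumptions, since the documents give none: dm is the chance that histology confirms a truly positive margin at a marked site, and du the same at an unmarked site.

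**1. The plan's own figure.** The cut-off is at least 13 of 14.
- At 0.70: 14 × 0.70^13 × 0.30 + 0.70^14 = 0.0407 + 0.0068 = 0.0475.
- At 0.95: 14 × 0.95^13 × 0.05 + 0.95^14 = 0.3593 + 0.4877 = 0.847.

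Both agree with section 8.4.

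**2. Which cells move.** Let T be the number of truly positive margins, F the truly negative margins that CVG calls positive, G the truly negative margins that CVG calls negative, and S the true sensitivity.
- n22 = T·S·dm
- n21 = F + T·S·(1 − dm)
- n13 = T·(1 − S)·du
- n11 = G + T·(1 − S)·(1 − du)

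dm appears only in the CVG-positive row. Raising it shifts tumours from n21 to n22 and leaves n11 and n13 alone.

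Example: T = 14, S = 0.70, du = 0.8, and 95% of the 74 truly negative margins called negative (F = 3.7, G = 70.3). Then n13 = 14 × 0.30 × 0.8 = 3.36 and n11 = 70.3 + 14 × 0.30 × 0.2 = 71.14 in both columns.

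| | dm = 0.8 (equal) | dm = 0.95 |
|---|---|---|
| n22 | 7.84 | 9.31 |
| n21 | 5.66 | 4.19 |
| Sensitivity | 0.700 | 0.735 |
| Specificity | 0.926 | 0.944 |
| PPV | 0.581 | 0.690 |
| NPV | 0.955 | 0.955 |
| n13/88 | 0.038 | 0.038 |

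**3. Apparent sensitivity.** It equals S·dm / (S·dm + (1 − S)·du). With S = 0.70, dm = 0.95 and du = 0.8: 0.665 / (0.665 + 0.240) = 0.735. When dm = du it equals S.

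**4. Chance of meeting the section 8.4 sizing criterion when true sensitivity is 0.70.** Three versions:
- (a) Exactly 14 confirmed positives, at least 13 required.
- (b) 14 truly positive margins. The number confirmed is binomial with probability 0.70·dm + 0.30·du, and the cut-off is reset to keep the level at or below 0.05 for the number confirmed (for example 13 of 13, 13 of 14, 14 of 15).
- (c) 88 patients with 15.5% positive on standard reading. The number confirmed is binomial with n = 88 and probability (0.155/du) × (0.70·dm + 0.30·du), with the same resetting.

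| dm | du | Apparent sensitivity | (a) | (b) | (c) |
|---|---|---|---|---|---|
| 0.95 | 0.95 | 0.700 | 0.0475 | 0.029 | 0.025 |
| 0.95 | 0.9 | 0.711 | 0.057 | 0.031 | 0.031 |
| 0.95 | 0.8 | 0.735 | 0.081 | 0.038 | 0.049 |
| 0.95 | 0.7 | 0.760 | 0.116 | 0.051 | 0.080 |
| 0.95 | 0.6 | 0.787 | 0.167 | 0.073 | 0.137 |

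Versions (b) and (c) start below 0.0475 because most cut-offs other than 13 of 14 have a smaller attained level. The comparison that matters is down each column.

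**The case against.** **The pathology is standard, and positives elsewhere still count.** True: section 8.1 says so, and attention to marked sites serves the location matching that the three-column table in 8.3.2 needs. No passage orders extra sections or levels there, so extra yield is an inference from the wording. But particular attention is by its terms something beyond the standard examination, and no rule makes the two readings equal. The bias could be offset if the closer look mainly overturned false-positive histology; nothing in the documents points that way.

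**The size is assumed.** This stands. For du of 0.8 to 0.9 the shift in sensitivity is only 1 to 4 points, and in versions (b) and (c) the chance of meeting the criterion stays below 0.05 at those values. Larger effects need standard histology to miss 30 to 40% of positive margins, for which the documents offer no support. In addition, the one-sided test against 0.70 appears only in the sample-size text; section 8.3.2 plans an estimate with a 95% confidence interval.

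**A reader might infer that NPV and n13/N are flattered too**, because foci missed at unmarked sites are filed under n11 instead of n13. The documents do not support that. Both cells are in the CVG-negative row, where section 8.2.2 puts no ink. Those specimens get the standard examination with or without the instruction, so such misses are ordinary imperfect histology. Only if absence of ink led to less than a standard reading would these quantities change. The test of n13/N against 15.5%, the only hypothesis test on margins in 8.3.2, is not affected.

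**A reader might also infer a proven conflict with standard of care.** Section 5.2.4 says: "Findings with the study will be recorded but will not change the standard of care", and section 8.1 bars interventions based on CVG results. No passage says how a positive found only through the CVG-directed look enters the clinical report, so this is a gap to reconcile and not a demonstrated contradiction.

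**Conclusion.** The point holds for sensitivity, specificity and PPV. As written, the reference standard depends on the index test, and the direction is upward whenever marked sites are read more completely than unmarked ones. The size cannot be derived from the documents. Under the assumed detection rates, a true sensitivity of 0.70 shows as 0.71 to 0.79. The chance of meeting the sizing criterion rises from 0.0475 to 0.057–0.167 with exactly 14 confirmed positives, or from 0.025–0.03 to about 0.03–0.14 when that number varies. NPV, n13/N and the comparison with 15.5% are outside the point, and the section 8.4 sensitivity calculation is correct on its own inputs.

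**What to change.** In section 8.1, define the primary reference as the margin result from the standard pathology work-up, recorded before the CVG findings are disclosed to the pathologist. Record CVG-positive locations on an oriented map or photograph of the specimen; section 5.2.4 already has all six aspects imaged. Apply any CVG ink needed for location matching or for the section 5.6.2 cores only after that result is recorded. Then release the map, allow the targeted review of marked sites, and report what it adds as a separate secondary analysis. Align sections 8.2.2 and 5.6.2 with this order.

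The sample size does not change. The cost is a modest workflow change. Inking moves later, core collection (5.6.2) and CVG imaging of the breadloafed slices (5.2.4) must be arranged so that they do not disclose the CVG call, and locations are matched by map, which is less direct than ink. Section 5.2.2 already allows for protocol revision before phase 2.

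Separately, the handling of a positive margin found only by the CVG-directed review must be reconciled with the statements in 5.2.4 and 8.1 that CVG results do not alter care. Recording the standard result first does not settle that question.

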8.2 Endpoints

8.2.1 Endpoints for Safety Analysis

The primary endpoints of the phase 1 portion of the trial are toxicities and/or adverse events (as outlined in the National Cancer Institute Common Terminology Criteria for Adverse Events version 5.0) recorded after LS301 injection which are definitively or possibly related to the injection. Safety evaluation includes vital signs, clinical laboratory testing and ECG, measured pre- (within 10-15 minutes or 30 minutes of injection) and post-injection (within 30 minutes or/and at ~60 minutes). Noteworthy post-versus-pre changes in all the safety measures will be recorded while clinically significant changes will be reported as adverse events in accordance to HRPO requirements. All the safety endpoints are described in detail in Section 5.4 and adverse events detailed in Section 6.0.

8.2.2 Endpoint for Prediction of Positive Margin and Positive SLN Analysis

The primary objective is to assess margin status called by LS301 and CVG in comparison to the gold standard histopathological results. The histopathological results of margin positivity has the following possible results: margin negative, margin positive at LS301 and CVG identified locations, margin positive at LS301 and CVG unidentified locations. Using LS301 and CVG, the exercised tissue will be considered to be margin positive and have ink marked at the identified locations if any positive margins are observed; otherwise, the margin is considered negative. Diagnostic test characteristics (sensitivity and specificity) of LS301 and CVG for margin positivity by histology will be established and margin positivity rate, defined as the proportion of tumors with histopathologically confirmed positive margins but missed by CVG, will be estimated. The secondary endpoint of the phase 2 trial is toxicity.

8.3 Data Analysis

Clinical and demographic characteristics of the participants will be summarized using descriptive statistics, overall and by dose levels.

8.3.1 Safety Analysis

Adverse events will be summarized by descriptive statistics (counts, percentages) overall and by dose level (if applicable). The post-injection vital signs will be separately compared to the pre-injection measurements by two-sample t-test or Wilcoxon rank sum test as appropriate, across all patients and by dose level (if applicable).

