5.4.1 Vital Signs

All vital signs will be recorded on the case report form. Vital signs may be obtained with the subject in the supine or upright position. Care will be taken to obtain subsequent recordings with the subject in the same position (supine or upright). Although allergic or other immediate adverse reactions are not anticipated, subjects will be monitored for at least 60 minutes post injection in an area where emergency equipment is available. Vital signs will be obtained pre-injection (within 30 minutes prior to injection of LS301), within 30 minutes post injection, at 60 minutes post injection, and prior to surgery. Vital signs will include the following: heart rate, systolic blood pressure, diastolic blood pressure, respiratory rate, and body temperature. The following changes from baseline will be considered noteworthy:

- Heart rate > 20 beats per minute
- Systolic blood pressure > 20 mm Hg
- Diastolic blood pressure > 10 mm Hg

Noteworthy changes will be documented on the CRF, and they will be marked as clinically significant or not. If clinically significant, the principal investigator will assess the causality of the change to the injection of LS301. Clinically significant changes in vital signs will be followed up hourly until they return to baseline or normal levels, or until follow-up is no longer warranted. If a clinically significant change of a vital sign is noted, it will be reported on the adverse event log.

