5.4.2 Clinical Laboratory Testing

Laboratory tests will consist of the following: standard CBC, comprehensive metabolic panel and urinalysis obtained at the following time points:

- Baseline: within 30 minutes prior to injection of LS301
- 60 minutes after injection of LS301
- Approximately one hour prior to surgery

Approximately 14 ml of blood and a urine sample will be collected at each time point. For patients enrolled in phase 1B and phase 2 of the study, a portion of the blood samples from each time point will be used to identify the predominant blood protein(s) that binds LS301 and mediates the bioavailability of the agent (refer to Section 5.6). Phase 1B refers to phase 1 study after completing drug safety and selecting optimal dose for testing at 2 and 4 hours from injection to surgery. The current project is that if 3 patients at each of the 3 dose level do not experience adverse events, we will need only 9 patients for the drug safety study (phase 1A) and additional 9 patients at the selected dose for testing at 2, 4, and >12 hours (3 patients for each time point) from injection to surgery.

The results of standard of care laboratory testing obtained up to 30 days post injection will be reviewed. Analysis of this will take into account that the subject has undergone surgical removal of tumor and neoadjuvant treatment including hormonal therapy or chemotherapy.

The following changes from baseline clinical laboratory values are considered to be noteworthy and require assessment as to clinical significance when they fall outside of normal limits. Clinically significant changes in laboratory values should be followed up daily until they return to baseline or normal levels, or until follow-up is no longer warranted. Laboratory values that are abnormal at baseline but move into normal range will not be considered clinically significant. If a clinically significant change of a laboratory value is noted, it will be reported on the AE log.

Analyte	Change from baseline
Hemoglobin	> 2g/dL
WBCs	> 1 K/mm ³
Neutrophils	> 10 %
Lymphocytes	> 10%
Platelets	> 50 K/mm ³
Creatinine	> 0.75 mg/dL
BUN	> 20 mg/dL
Calcium	> 1mg/dL
Sodium	> 5 mmol/L
Potassium	> 0.5 mmol/L
CO ₂	> 4 mmol/L
ALT (SGPT)	> 150 IU/L
AST (SGOT)	> 100 IU/L
Alkaline Phosphatase	> 150 IU/L
Total Bilirubin	> 0.5 mg/dL
Albumin	> 1g/dL

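### Section 8.3.1 names independent-samples tests for pre- and post-injection vital signs from the same patients; the comparison should be paired and reported as mean or median change with a confidence interval

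*Combined protocol and SAP*

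**What the plan says.** Section 8.3.1 gives one inferential method for safety data: post-injection vital signs are "compared to the pre-injection measurements by two-sample t-test or Wilcoxon rank sum test as appropriate, across all patients and by dose level", with a note that dose level applies where relevant. Adverse events are summarised by counts and percentages.

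Section 5.4.1 describes how the data arise: "Vital signs will be obtained pre-injection (within 30 minutes prior to injection of LS301), within 30 minutes post injection, at 60 minutes post injection", and again before surgery. It asks that a patient's later recordings be made in the same position as the earlier ones, and it defines limits under the words "The following changes from baseline will be considered noteworthy". Section 8.2.1 uses the same idea: "Noteworthy post-versus-pre changes in all the safety measures will be recorded".

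On numbers, section 8.1 allows escalation from three patients upwards ("dose escalation occurs when 3/3, 4/4, 5/5, 5/6 or 6/6 patients are evaluated without DLT"). Section 5.4.2 projects that "if 3 patients at each of the 3 dose level do not experience adverse events, we will need only 9 patients" for phase 1A, followed by 9 more in phase 1B.

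**The concern.** The plan collects each patient's own baseline and defines the safety measure as a change from it. It then names two tests that treat the pre- and post-injection values as if they came from different people. Loose wording does not explain this. The rank sum test is the independent-samples test, and its paired counterpart is the signed-rank test. The phrase about appropriateness only chooses between the two tests named. No section mentions a paired test, a repeated-measures model or a control group.

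What is at stake is the group-level reading of vital signs in a first-in-human study. Readings taken from one person within about an hour are plausibly positively correlated. If so, the named tests are too conservative, and for a safety comparison that is the unhelpful direction.

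**Working it through.** The plan states no power, alpha, SD or correlation for this comparison, so it has no figure to reproduce. The inputs below are therefore part document, part assumption.

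**From the documents.** Dose levels hold 3 to 6 patients (8.1). Phase 1 totals 9 + 9 = 18 under the projection in 5.4.2. Phase 2 has 88 (5.2.2).

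**Assumed.** Normal readings with equal SD before and after; correlation ρ from 0 to 0.8; true shift 0.8 SD; two-sided 5% level.

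**Standard error.** The variance of the mean change is 2σ²(1−ρ)/n. The unpaired test uses 2σ²/n. The unpaired standard error is therefore 1/√(1−ρ) times the correct one: 1.00 at ρ = 0, 1/√0.7 = 1.20 at 0.3, 1/√0.5 = 1.41 at 0.5 and 1/√0.2 = 2.24 at 0.8.

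**t-tests.** Simulation with 100,000 datasets per setting, pooled two-sample t against paired t. Entries are power for a 0.8 SD shift, unpaired / paired.

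| n | ρ = 0 | ρ = 0.3 | ρ = 0.5 | ρ = 0.8 |
|---|---|---|---|---|
| 3 | 0.12 / 0.09 | 0.10 / 0.11 | 0.09 / 0.14 | 0.08 / 0.25 |
| 6 | 0.24 / 0.20 | 0.21 / 0.27 | 0.19 / 0.36 | 0.16 / 0.70 |
| 18 | 0.64 / 0.62 | 0.67 / 0.77 | 0.70 / 0.89 | 0.77 / 0.999 |

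At n = 88 both powers exceed 0.99.

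**True size of the unpaired t-test at nominal 0.05**, for ρ = 0, 0.3, 0.5, 0.8:
- n = 6: 0.050, 0.025, 0.013, 0.002
- n = 18: 0.050, 0.021, about 0.007, 0.0001

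The paired test stays at about 0.05 throughout.

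**Rank tests.** 40,000 datasets per setting with exact distributions, 0.8 SD shift, rank sum / signed-rank:
- n = 18: 0.65 / 0.88 at ρ = 0.5; 0.73 / 0.999 at ρ = 0.8
- n = 6: 0.16 / 0.24 at ρ = 0.5; 0.14 / 0.52 at ρ = 0.8

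**Expected 95% interval half-width** (t quantile × standard error × E[s]/σ), in SD units:
- n = 18: 0.67 unpaired; 0.49 (ρ = 0.5) or 0.31 (ρ = 0.8) paired
- n = 88: 0.30 unpaired; 0.21 or 0.13 paired
- n = 3: 2.13 unpaired (its ρ = 0 value); 2.20 (ρ = 0.5) paired, because only 2 degrees of freedom remain

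**Smallest attainable two-sided signed-rank p** = 2/2ⁿ: 0.25 at n = 3, 0.125 at n = 4, 0.0625 at n = 5, 0.031 at n = 6. With five or fewer patients the signed-rank test cannot reach 0.05.

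**The case against.** The strongest reply is that nothing turns on this test. Escalation and stopping use DLT counts (8.1, 8.5). Each patient's vital signs are screened against that patient's own baseline (5.4.1). Clinically significant changes become adverse events (8.2.1). All of that stands, and it limits the weight of the point.

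The gap also depends on n, and 18 is only a projection. With six patients at each of three levels, phase 1 would total 18 + 9 = 27, and power for 0.8 SD at ρ = 0.5 would be 0.90 against 0.98. If all patients means both phases (18 + 88 = 106, or 27 + 88 = 115), both tests detect 0.8 SD almost surely. A gap then remains only for smaller shifts: 0.61 against 0.86 for 0.3 SD at n = 106, ρ = 0.5. This stands too.

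Pairing also has a cost at the smallest levels. At n = 3 the paired interval is wider on average unless ρ exceeds about 0.53; the break-even is about 0.36 at n = 4 and 0.27 at n = 5. That is a reason to expect little from such levels. It does not justify the unpaired interval, whose coverage is wrong when ρ is not zero.

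Finally, section 8.3.1 promises no intervals, so asking for them is a reporting addition separate from the wrong test. Dropping the p-value at small levels is a convention: a t-based 95% interval excludes zero exactly when the paired t-test gives p < 0.05. Both remarks are fair, and neither defends the tests named.

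**Conclusion.** The concern holds. As written, section 8.3.1 applies independent-samples tests to paired data. With positive within-patient correlation the result is a conservative test. In the projected 18 phase 1 patients, a 0.8 SD shift would be detected with power 0.70 instead of 0.89 at ρ = 0.5, and the true error rate would be about 0.007 instead of 0.05. These sizes rest on an assumed shift and correlation. At ρ = 0 there is no loss, and at 88 patients only precision changes for a shift of that size. The consequence is confined to the supplementary vital-sign comparison and touches no dose decision, stopping rule or sample size. The correction should still be made, because the specification is wrong and the remedy costs almost nothing.

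**What to change.** In section 8.3.1 replace the test sentence with:

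*At each post-injection time, the within-patient change from the pre-injection value will be summarised as mean or median change with 95% confidence interval and compared with zero by paired t-test or Wilcoxon signed-rank test, across all patients and by dose level. For dose levels with five or fewer patients, only the estimate and t-based 95% confidence interval of the mean change will be reported.*

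The change of test is the essential part. The second sentence is a reporting choice suited to levels of 3 to 5 patients. If the pre-surgery reading is analysed, report it separately, since it may reflect pre-operative conditions.

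The cost is two sentences, with no new data, visits or patients. Section 5.2.2 already foresees protocol revisions before phase 2, which gives a natural occasion.
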